9.6.8 Concomitant medications

Details of all concomitant medications taken throughout the course of the study will be collected at every visit, phone contacts, and Unscheduled Visits. Ongoing concomitant medications from C87035 will continue to be followed in CR0012.

9.6.9 Medications for CD

Details of medication taken for the treatment of CD will be recorded throughout the study at scheduled site visits and via phone calls by the Investigator (designee) at every 4 week intervals between regular visits. In addition, information on medication taken as maintenance treatment for CD will be recorded throughout the study.

9.6.10 Autoantibodies

Autoantibody (ANA and anti-dsDNA) titers will be determined every 12 weeks starting at Week 14, and at the Completion/ET and SFU Visits.

Instructions on blood sample collection, processing, storage, and shipping will be provided in the laboratory manual for this study.

10 EFFICACY ASSESSMENTS

10.1 Disease activity/PCDAI

The subjects' disease activity will be assessed using the PCDAI. The PCDAI was developed by pediatric inflammatory bowel disease (IBD) experts and was validated at 12 North American institutions (Hyams et al, 1991). It is a modification of the Clinical Disease Activity Index (CDAI) which is the accepted instrument to measure CD disease activity in clinical studies with adults. The PCDAI consists of 4 domains (laboratory, height/weight, examination, and history) with several assessments that are converted into a PCDAI score which can range from 0 to 100 points with a higher score indicating more severe disease activity. In comparison to the CDAI, the PCDAI decreases the weighting given to subjective historical terms, adds height velocity, and adds ESR to the laboratory measures included (Hyams et al, 1991; Otley et al, 1999). The PCDAI is provided in [Section 17.2](#).

The Investigator will calculate the subjects' PCDAI scores every 12 weeks starting at Week 14, and at the Completion/ET Visit. Calculation of PCDAI scores is also necessary to determine whether a subject loses response (Section 5.1). For subjects undergoing reinduction, PCDAI scores will be calculated at Reinduction Weeks 0, 2, and 4.

For the calculation of the PCDAI score at a particular visit (to assess efficacy of CZP treatment), values for hematocrit, ESR, and albumin are used from the same clinic visit. Thus, the PCDAI score calculation cannot be completed until the laboratory values have been received at the site.

Since portions of the PCDAI calculations are based upon a 1-week (7-day) history recall of symptoms, subjects and/or caregivers will be contacted prior to the visit with a reminder that this information needs to be provided at the visit.

10.2 Erythrocyte sedimentation rate

The ESR will be assessed every 12 weeks starting at Week 14, and at the Completion/ET Visit. Results of these measurements form part of the PCDAI assessments described in Section 10.1.

For subjects undergoing reinduction, ESR will be assessed at Reinduction Weeks 0, 2, and 4.

Instructions on blood sample collection, processing, storage, and shipping will be provided in the laboratory manual for this study.

10.3 C-reactive protein

Levels of CRP will be assessed every 12 weeks starting at Week 14, and at the Completion/ET Visit.

Instructions on blood sample collection, processing, storage, and shipping will be provided in the laboratory manual for this study.

10.4 Tanner stage

Assessments of subjects' developmental stages will be performed to determine the subjects' Tanner stages (Marshall and Tanner, 1969; Marshall and Tanner, 1970). These assessments will be performed every 12 weeks starting at Week 14, and at the Completion/ET Visit.

10.4.1 Bone markers

Markers of bone and collagen turnover, reflecting the childhood growth curve, will be measured at Weeks 14, 26, 38, 50 and then every 12 months thereafter, and at the Completion/ET Visit. These markers will include: osteocalcin, bone specific alkaline phosphatase, and n-telopeptides. Tests will be performed by a central laboratory facility.

Instructions on blood sample collection, processing, storage, and shipping will be provided in the laboratory manual for this study.

10.5 Height

Height will be recorded every 12 weeks starting at Week 14, and at the Completion/ET Visit. Height will be recorded after the shoes have been removed. Height should preferably be

measured with a wall-mounted stedometer. Results of these measurements form part of the PCDAI assessments described in [Section 10.1](#).

10.6 Weight

Weight will be recorded after removal of shoes and heavy clothing. Weight will be measured every 12 weeks starting at Week 14, and at the Completion/ET Visit.

Results of the weight measurement will be used to determine the subject's CZP dose as specified in [Table 7-1](#). In addition, results of these measurements form part of the PCDAI assessments described in [Section 10.1](#).

10.7 IMPACT-III

The IMPACT questionnaire is a disease-specific health-related quality of life (HRQOL) questionnaire for use in children with IBD that was originally developed and validated by a Canadian team (Griffiths et al, 1999; Otley et al, 2002). The IMPACT-III, a modified version of the original questionnaire, contains 35 questions assessing the following 6 domains: bowel symptoms, systemic symptoms, emotional functioning, social functioning, body image, and treatment/interventions. For each question, there are 5 Likert response options. Total IMPACT-III scores range from 35 to 185 with higher scores indicating better HRQOL. This questionnaire will be used to assess HRQOL of all subjects; however, it has only been validated for children aged ≥ 10 years in North America. The IMPACT-III questionnaire is provided in [Section 17.3](#). The IMPACT-III questionnaire will be administered at Weeks 14, 26, 38, 50 and then every 12 months thereafter, and at the Completion /ET Visit.

For subjects undergoing reinduction, the IMPACT-III questionnaire will be administered at Reinduction Week 0.

The IMPACT-III questionnaire is a copyright of the Pediatric Inflammatory Bowel Disease Working Group on Quality of Life (copyright 2002). The IMPACT-III has been provided under licences, by the Pediatric Inflammatory Bowel Disease Working Group and must not be copied, distributed, or used in any way without prior written permission by the Pediatric Inflammatory Bowel Disease Working Group.

10.8 Days missed from school/work (WPAI:CD for children and for working individuals with CD)

The Work Productivity and Activity Impairment Questionnaire for children with CD (WPAI:CD) is used to [REDACTED]

[REDACTED] If a subject has left school and is working, the WPAI:CD for working individuals is used instead of the WPAI:CD for children. If a subject is both attending school and working, both the WPAI:CD for children and the WPAI:CD for working individuals are used.

The WPAI:CD for children questionnaire contains 6 questions: [REDACTED]

[REDACTED], all 6 questions are completed, and [REDACTED]

[REDACTED], the subject completes only question number 6 to [REDACTED]. The 6 items are regrouped into 4 dimensions and the scores are expressed as percentages, with higher numbers indicating greater impairment and less productivity (Reilly et al, 2008).

The WPAI:CD for working individuals questionnaire contains 6 questions: [REDACTED]

The WPAI:CD for children questionnaire is administered to all subjects or the parent(s)/legally acceptable representative(s) and the WPAI:CD for working individuals questionnaire is only administered to subjects who work, under supervision of the Investigator or designee at Weeks 14, 26, 38, 50 and then every 12 months thereafter, and at the Completion /ET Visit.

For subjects undergoing reinduction, the WPAI:CD questionnaires will be administered at Reinduction Weeks 0 and 4.

The WPAI:CD questionnaire for children with CD (Section 17.4) and the WPAI:CD for working individuals are provided (Section 17.5).

10.9 Effect on the caregiver's work (WPAI:CD for caregivers)

The WPAI:CD questionnaire for caregivers of children with CD is used to [REDACTED]

[REDACTED] he questionnaire contains 6 questions:

[REDACTED] all 6 questions are completed, and if [REDACTED], the caregiver completes only question number 6 to reflect [REDACTED]. The 6 items are regrouped into 4 dimensions and the scores are expressed as percentages, with higher numbers indicating greater impairment and less productivity.

The questionnaire is administered under supervision of the Investigator or designee to the caregiver at Weeks 14, 26, 38, 50 and then every 12 months thereafter, and at the Completion/ET Visit.

For subjects undergoing reinduction, the WPAI:CD questionnaire will be administered at Reinduction Weeks 0 and 4.

The WPAI:CD questionnaire for caregivers of children with CD is provided in Section 17.6.

10.10 Concurrent medical procedures

Any concurrent medical procedures will be recorded throughout the course of the study at every visit, phone contacts, and Unscheduled Visits.

11 PHARMACOKINETICS AND IMMUNOLOGICAL ASSESSMENTS

Blood samples will be collected to determine plasma concentrations of CZP and anti-CZP antibodies every 12 weeks starting at Week 14, and at the Completion/ET and SFU Visits. All of these blood draws will be performed prior to study drug administration (except for the Completion/ET and SFU Visits when there is no dosing) and all of them coincide with the blood collection times for the assessment of hematology and clinical chemistry parameters, so that no additional blood sampling is required at these visits.

Time and date of each blood draw will be documented on the CRF.

Instructions on blood sample collection, processing, storage, and shipping will be provided in the laboratory manual for this study.

12 STUDY MANAGEMENT AND ADMINISTRATION

12.1 Adherence to protocol

The Investigator should not deviate from the protocol. In medical emergencies, the Investigator may use his/her medical judgment and may remove a study participant from immediate hazard before notifying UCB (or its representative) and the IRB/IEC in writing regarding the type of emergency and the course of action taken.

12.2 Monitoring

UCB (or designee) will monitor the study to meet the Sponsor's monitoring Standard Operating Procedures (SOPs), ICH-GCP guidelines, and applicable regulatory requirements, and to ensure that study initiation, conduct, and closure are adequate. Monitoring of the study may be delegated by UCB to a contract research organization (CRO) or a contract monitor.

The Investigator and his/her staff are expected to cooperate with UCB (or designee) and to be available during the monitoring visits to answer questions sufficiently and to provide any missing information. The Investigator(s)/institution(s) will permit direct access to source data/documents for study-related monitoring, audits, IRB/IEC review, and regulatory inspection(s).

The Investigator will allow UCB (or designee) to periodically review all CRFs and corresponding source documents (eg, hospital and laboratory records for each study participant). Monitoring visits will provide UCB (or designee) with the opportunity to evaluate the progress of the study, verify the accuracy and completeness of CRFs, ensure that all protocol requirements, applicable authorities regulations and Investigator's obligations are being fulfilled, and resolve any inconsistencies in the study records.

12.2.1 Definition of source data

All source documents must be accurate, clear, unambiguous, permanent, and capable of being audited. They should be made using some permanent form of recording (ink, typing, printing, optical disc). They should not be obscured by correction fluid or have temporary attachments (such as removable self-stick notes). Photocopies of CRFs are not considered acceptable source documents. Source documents are original records in which raw data are first

recorded. These may include hospital/clinic/general practitioner records, charts, diaries, x-rays, laboratory results, printouts, pharmacy records, care records, ECG or other printouts, completed scales, or Quality of Life Questionnaires, for example. Source documents should be kept in a secure, limited access area.

The following data will be recorded directly in the CRF and will not appear in a source document as defined above: IMPACT-III and WPAI:CD.

Source documents that are computer generated and stored electronically must be printed for review by the monitor (eg, ECG reports). Once printed, these copies should be signed and dated by the Investigator and become a permanent part of the subject's source documents. The Investigator will authorize the monitor to compare the content of the printout and the data stored in the computer to ensure all data are consistent.

Electronic data records such as holter monitor records or electroencephalogram records must be saved and stored as instructed by UCB (or designee).

12.2.2 Source data verification

Source data verification ensures accuracy and credibility of the data obtained. During monitoring visits reported data are reviewed with regard to being accurate, complete, and verifiable from source documents (eg, subject files, recordings from automated instruments, tracings [ECG], x-ray films, laboratory notes). All data reported on the CRF should be supported by source documents, unless otherwise specified in Section 13.2.1.

12.3 Data handling

12.3.1 Case report form completion

The Investigator is responsible for prompt reporting of accurate, complete, and legible data in the CRFs and in all required reports.

Any change or correction to the CRF should be dated, initialed, and explained (if necessary) and should not obscure the original entry. Use of correction fluid is not permitted.

Corrections made after the Investigator's review and signature of the completed CRF will be resigned and dated by the Investigator.

The Investigator should maintain a list of personnel authorized to enter data into the CRF.

Detailed instructions will be provided in the CRF completion guidelines.

12.3.2 Database entry and reconciliation

Case report forms/external electronic data will be entered/loaded in a validated electronic database using a clinical data management system (CDMS). Computerized data cleaning checks will be used in addition to manual review to check for discrepancies and to ensure consistency of the data. Case report form data are entered into the clinical database using independent, double-data entry, with the exception of comment fields, which are verified by a second person.

An electronic audit trail system will be maintained within the CDMS to track all data changes in the database once the data has been saved initially into the system or electronically loaded. Regular backups of the electronic data will be performed.

12.3.3 Subject Entry and Enrollment log/Subject Identification Code list

The subject's entry and enrollment will be recorded in the Subject Entry and Enrollment Log.

The Investigator will keep a Subject Identification Code list. This list remains with the Investigator and is used for unambiguous identification of each subject.

The subject's consent and enrollment in the study must be recorded in the subject's medical record. These data should identify the study and document the dates of the subject's participation.

12.4 Termination of the study

Upon completion of the study, the monitor will conduct the following activities in conjunction with the Investigator, as appropriate:

- Return of all study data to UCB or its representatives while maintaining original source documents
- Data clarification and/or resolution
- Accountability, reconciliation, and arrangements for used and unused investigational products
- Review of site study records for completeness
- Discussion/reminder on archiving responsibilities
- Discussion of IRB/IEC requirements for study termination
- Arrangements for unused CRFs, lab supplies, and any other study related supplies

UCB reserves the right to temporarily suspend or prematurely discontinue this study either at a single site, multiple sites, or at all sites at any time for reasons including, but not limited to, safety or ethical issues, inaccurate or incomplete data recording, noncompliance, or unsatisfactory enrollment with respect to quality or quantity.

If the study is prematurely terminated or suspended, UCB (or its representative) will inform the Investigators/institutions, and the regulatory authority(ies) of the termination or suspension and the reason(s) for the termination or suspension, in accordance with applicable regulatory requirement(s). The IRB/IEC should also be informed and provided with reason(s) for the termination or suspension by the Sponsor or by the Investigator/institution, as specified by the applicable regulatory requirement(s). In addition, arrangements will be made for the return of all unused investigational products and other material in accordance with UCB procedures for the study.

12.5 Archiving and data retention

The Investigator will maintain adequate records for the study including CRFs, medical records, laboratory results, Informed Consent documents, drug dispensing and disposition records, safety reports, information regarding participants who discontinued, and other pertinent data.

All essential documents are to be retained by the Investigator until at least 2 years after the last approval of a marketing application in an ICH region and until there are no pending or contemplated marketing applications in an ICH region, or at least 2 years have elapsed since the formal discontinuation of clinical development of the investigational product. These documents should be retained for a longer period, however, if required by the applicable regulatory requirement(s) or by an agreement with UCB (ICH-GCP Guideline, Section 4.9.5). The Investigator will contact UCB for authorization prior to the destruction of any study records or in the event of accidental loss or destruction of any study records. The Investigator will also notify UCB should he/she relocate or move the study-related files to a location other than that specified in the Sponsor's study master file.

12.6 Audit and inspection

The Investigator will permit study-related audits mandated by UCB and inspections by domestic or foreign regulatory authorities, after reasonable notice.

The main purposes of an audit or inspection are to confirm that the rights and well-being of the subjects enrolled have been protected, that enrolled subjects (ie, signing consent and undergoing study procedures) are appropriate for the study, and that all data relevant for the evaluation of the IMP have been processed and reported in compliance with the planned arrangements, the protocol, investigational site, and IRB/IEC SOPs, ICH/GCP, and applicable regulatory requirements.

The Investigator will provide direct access to all study documents, source records, and source data. If an inspection by a regulatory authority is announced, the Investigator will immediately inform UCB (or designee).

12.7 Good Clinical Practice

Noncompliance with the protocol, ICH/GCP, or local regulatory requirements by the Investigator, institution, institution staff, or designees of the Sponsor will lead to prompt action by UCB to secure compliance. Continued noncompliance may result in the termination of the site's involvement in the study.

13 STATISTICS

A description of statistical methods is presented below and will be described in more detail in the Statistical Analysis Plan (SAP).

13.1 Definition of analysis sets

The All Subject Population will include those subjects who are enrolled in the study. All available data entered into the database will be listed for this population.

The Safety Population will include all subjects enrolled who receive at least 1 injection of study treatment in this study. This population will be used to summarize the safety, PK, and immunological variables.

The Intention-to-Treat (ITT) Population will include all subjects irrespective of any protocol deviations who receive at least 1 injection of study treatment in this study and who have at least 1 efficacy measurement after the first injection of this study. This population will be used to summarize the efficacy variables.

13.2 General statistical considerations

Summary statistics will consist of sample size, frequencies, and corresponding percentages for categorical variables. For continuous variables, descriptive statistics (number of available observations, mean, median, standard deviation, minimum, and maximum) will be tabulated. Data summarized by visit will use nominal visits with the exception of data collected at withdrawal visits which will be summarized at the next scheduled nominal visit dependent on when the withdrawal visit occurs taking into account the allowable visit windows.

Summaries will be by treatment received at the end of C87035. Any other subgroups of interest such as subjects who have been reinduced in C87035 or reinduced during CR0012 will be detailed in the SAP.

For data such as Crohn's disease history which are only collected at the Screening Visit of C87035, these will be defined as the Baseline values. For data which are collected at Week 0 of C87035 and prior to receiving any study treatment, the last nonmissing value prior to receiving any treatment will be defined as the Baseline values.

All analyses will be performed using the SAS software package.

All AEs will be coded and classified by primary System Organ Class (SOC) and Preferred Term (PT) according to the most recent version of the Medical Dictionary for Regulatory Activities (MedDRA[®]).

All medications will be coded using World Health Organization Drug (WHODrg).

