Single intravenous (iv) and subcutaneous (sc) doses of CZP in healthy volunteers have been shown to have a predictable dose-related response with an approximately linear relationship between the dose administered and the maximum serum concentration (C_{max}) and the area under the CZP plasma concentration versus time curve (AUC). The terminal elimination phase half-life ($t_{1/2}$) was approximately 14 days for all dosage levels tested and the bioavailability of CZP when administered subcutaneously was approximately 80%. A similar PK profile was found in healthy Japanese and Caucasian subjects. The metabolism and route of excretion of CZP have not yet been fully elucidated.

The safety of CZP has been assessed in 2518 adult subjects with CD representing over 2837 patient years of exposure. Certolizumab pegol is well tolerated. The incidence of injection site reactions and hypersensitivity-type reactions was low. There were no reports of anaphylaxis or anaphylactoid-type reactions with CZP. All available data in CD show the safety of CZP is consistent with the known risks of anti-TNF therapies.

The risks of the present study are essentially those of experiencing an adverse effect following administration of CZP and for loss of response. As a therapeutic class, currently available TNF-antagonists are known to be associated with serious infections, particularly reactivation of tuberculosis (TB) and opportunistic fungal infections. An association has also been reported with TNF-antagonist therapy and the development of lymphoma and leukemia especially in children and adolescents, although it is not clear whether there is a causal relationship as confounding factors exist (eg, the increased risk of lymphoma and leukemia associated with autoimmune diseases and immunosuppression) themselves. Other cancer types also have been reported in association with TNF-antagonist use, but the causal relationship for these is unclear as well. Other serious AEs that have been infrequently reported in subjects treated with currently available TNF-antagonists (including CZP) include congestive heart failure, drug-induced lupus, new-onset psoriasis, seizures, demyelinating disorders, and pancytopenia.

For more information, please refer to the Investigator's Brochure.

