5 STUDY DESIGN

5.1 Study description

This is a Phase 2, open-label, multicenter study in children and adolescents with moderately to severely active CD who completed C87035, or were terminated from C87035 when the study was stopped by UCB, to assess the longterm safety and tolerability of CZP.

All subjects who complete Week 62 of C87035 or were terminated from C87035 when the study was stopped by UCB (and completed all assessments required for Week 62/Visit 23 at the time of termination) are eligible for entry.

Subjects may continue on CZP at the dose they were receiving at the end of C87035 (Low-Dose Group or High-Dose Group [weight adjusted in kg; see [Section 7.2](#) and [Table 7-1](#)]) every 4 weeks until the subject reaches the age of 18 years or CZP is approved for use in the US by pediatric subjects with CD. The first clinic visit should coincide with the last visit of C87035 (Week 62/Visit 23). First study drug administration occurs 2 weeks later (Week 2) and subsequent clinic visits for safety and efficacy assessments are scheduled at 12-week intervals. After Week 2, subjects or parents/caregivers/appropriate designee as determined by the Investigator have the option of home administration of CZP upon appropriate training during a previous clinic visit(s) or continuing to have CZP administered every 4 weeks at the clinic. For subjects performing home administration, a phone call to the subject and/or the parents/caregiver will be performed by the Investigator (or designee) every 4 weeks between regular clinic visits in order to capture potential AEs and changes in concomitant medications, and to check compliance with home dosing. An SFU Visit will be conducted 12 weeks after the last dose of study medication for subjects.

Please refer to Study Schedule of Assessments in [Section 5.2](#) for visit-specific procedures and to [Section 5.3](#) for a schematic representation of the study.

A DSMB will periodically review all emerging safety data (see [Section 13.8](#)). Based on the safety data, the DSMB can recommend modifying or stopping the study.

Loss of response/reinduction

- *Subjects who were reinduced in C87035 are not eligible for reinduction in CR0012. Should loss of response occur in CR0012, the subject must be withdrawn.*
- *If there was no reinduction in C87035, 1 reinduction only is permitted in CR0012. If response is lost a second time in CR0012, the subject must be withdrawn.*

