^bAfter Week 2, subjects or parents/caregivers have the option of home administration of CZP upon appropriate training during a previous clinic visit(s) or can continue to have CZP administered every 4 weeks at the clinic. For subjects performing home administration, a phone call to the subject and/or the parents/caregiver will be performed by the Investigator (or designee) every 4 weeks between regular clinic visits in order to capture potential AEs and changes in concomitant medications, and to check compliance with home dosing. Subjects will have the option to either switch to home dosing or switch

Table 5-1. Schedule of study assessments

Visit or phone call (+/-7 days)	Treatment Period						
	Entry ^a	Visit	Phone call (home administration) or visit (clinic administration) ^b	Regular Clinic Visits ^b	Completion/Early Termination	Unscheduled Visit ^c	SFU ^d
Week	0	2	Every 4 weeks beginning at Week 6 and in between regular clinic visits	Every 12 weeks beginning at Week 14			+12 weeks after last dose of study drug

back to site administration at anytime during the study.

^cVital signs, concomitant medication, and AEs must be assessed at every Unscheduled Visit. Other safety and PK assessments (eg, CZP plasma sample) may be performed at the discretion of the Investigator as related to the nature of the visit.

^dThe SFU Visit should be performed 12 weeks after the final dose of study medication. For subjects continuing directly onto commercial CZP, a SFU Visit should be completed prior to the first dose of commercial drug administration.

^eFor all females post menses, a urine pregnancy test will be conducted at all regularly scheduled clinic visits except Week 2.

^fVital signs will be collected 15 minutes prior to dosing with a ± 5 minute window.

^gDays missed from school will be assessed using the WPAI:CD for children. The time missed from work will be assessed using the WPAI:CD for working individuals with CD. The effect of the child's CD on the caregiver's productivity will be assessed using the WPAI:CD for caregivers of children with CD.

^hPlasma samples will be collected to determine the concentration of CZP every 12 weeks starting at Week 14, and at the Completion/Early Termination and SFU Visits. Samples will be collected before dosing (except for the Completion/ET and SFU Visits when there is no dosing).

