8 STUDY PROCEDURES BY VISIT

During the study, the acceptable window between the study visits is +/-7 days relative to entry (Week 0).

8.1 Entry Week 0

Week 0 of CR0012 is equivalent to Week 62 of C87035 with the exceptions noted below. Subjects who were terminated from C87035 when the study was stopped by UCB completed all assessments required for Week 62/Visit 23 at the time of termination.

Before any study-related procedures are performed, an IRB/IEC approved informed consent will be properly executed and documented. The written informed consent of the child's parent(s)/legally acceptable representative(s) must be obtained. In addition, where requested by local laws or by the IRB/IEC and according to the child's age/competence, the Assent form should be obtained from the child. The subjects and their parent(s)/legally acceptable representative(s) will be given adequate time to consider any information concerning the study given to them by the Investigator or designee. As part of the informed consent procedure, subjects and their parent(s)/legally acceptable representative(s) will be given the opportunity to ask the Investigator any questions regarding potential risks and benefits of participation in the study.

Assessments to be performed include:

- Written informed consent
- Inclusion/ exclusion criteria
- Demography
- TB test
- TB questionnaire

The following ongoing information must be continued to be followed from C87035 to CR0012:

- Adverse events
- Concomitant medications

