10 PHARMACOKINETICS AND PHARMACODYNAMICS

10.1 Pharmacokinetics

Plasma concentrations of CZP at each visit will be summarized by anti-CZP antibody status (all subjects, antibody-positive, and antibody negative) for each age category, the overall population, and for each dose group. In addition, plasma concentrations will be summarized by weight category (<40kg; ≥40kg) for the treatment groups.

Individual anti-CZP antibody concentrations will be listed and the incidence of anti-CZP antibody positive subjects will be summarized by study visit and overall incidence by age category and by dose group. Anti-CZP antibody positive status is defined as a subject having a value >2.4 units/mL anti-CZP antibody at any time during the study. If there are more than 1 concentration available for the same timepoint, data will be listed as per the guidance found in the global convention document.

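### Protocol 13.2 moves Early Termination data to the next nominal visit with no exception for PK, so a CZP concentration taken at no fixed time after dosing can be averaged with predose troughs.

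*Protocol*

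**What the plan says.** Four provisions meet on this point.

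- **Mapping.** Protocol 13.2 summarizes by nominal visit, but treats separately "data collected at withdrawal visits which will be summarized at the next scheduled nominal visit dependent on when the withdrawal visit occurs". The sentence goes on to mention allowable visit windows. It names no variable to which the mapping does not apply.
- **Sampling.** Protocol 11 states: "Blood samples will be collected to determine plasma concentrations of CZP and anti-CZP antibodies every 12 weeks starting at Week 14", and also at the Completion/ET and Safety Follow-Up (SFU) visits. Draws precede dosing, "except for the Completion/ET and SFU Visits when there is no dosing". Footnote h of Table 5-1 says the same.
- **Timing of the ET visit.** Table 5-1 gives no week for the Completion/ET column and does not tie it to the last dose. Only the SFU visit is fixed, at 12 weeks after the last dose.
- **Analysis.** SAP 10.1 plans: "Plasma concentrations of CZP at each visit will be summarized by anti-CZP antibody status", also by age category, dose group and weight category. Protocol 13.5 plans the same and adds plots. Neither sets a condition on time since dose or says where ET or Completion concentrations belong. The nearest rule in SAP 10.1 concerns the listing of more than one concentration at the same timepoint.

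**The concern.** A by-visit concentration table can be read as an exposure profile only if the samples in a cell were taken at about the same point of the dosing interval. The predose rule secures this, approximately, for regular visits. The mapping rule can undo it, because a sample drawn at an arbitrary time after the last dose takes the label of a visit whose other samples are troughs. A high or low visit mean may then reflect when a leaving subject was sampled rather than drug exposure.

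PK is a secondary objective, and the concentration summaries are the only analysis of CZP levels that the SAP plans. Population PK modeling, which could use actual sampling times, is optional under Protocol 13.5 and would be reported separately. SAP 4.4 gives the study size as 16 subjects. Once these are split by antibody status, dose, age or weight, a single value carries real weight in a cell.

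**Working it through.** The plan states no concentration or expected trough, so there is no figure to reproduce. The check has two steps: when an ET sample joins troughs, and how far it can move a summary.

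**Step 1: which cell receives the ET sample.** PK visits fall at Weeks 14, 26, 38 and so on; 4-weekly contacts without PK sampling fall between them (Weeks 6, 10, 18, 22 and so on).

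- If only PK visits count as the next visit, every ET sample taken between two of them joins the later one.
- If the 4-weekly contacts also count, only ET samples from the last 4 of each 12 weeks join a PK visit, for example those after Week 22 and up to Week 26. The rest land in cells where no concentration is scheduled.

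The visit-window qualifier may shift these boundaries by days. It concerns visit dates, not time since dose. Pooling with troughs therefore occurs under both readings, but more often under the first.

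**Step 2: size.** Inputs from the documents: 4-weekly dosing, so a reference trough at day 28, and a terminal half-life that "was approximately 14 days for all dosage levels tested" (Protocol 2, healthy volunteers). Assumptions not in the documents: first-order decline throughout, absorption ignored, equal true exposure in all subjects, and ET samples at 14, 42 or 56 days after the last dose. The day-84 SFU visit is taken as the outer limit.

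Ratio to trough: C(t)/C(28) = 2^((28 - t)/14).

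- Day 14: 2^(14/14) = 2.0
- Day 42: 2^(-14/14) = 0.5
- Day 56: 2^(-28/14) = 0.25

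With one ET sample among n values and the others at trough, the shift in the arithmetic mean is (ratio - 1)/n:

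| n in cell | ET at day 14 | ET at day 42 | ET at day 56 |
|---|---|---|---|
| 4 | +25.0% | -12.5% | -18.8% |
| 8 | +12.5% | -6.2% | -9.4% |
| 16 | +6.2% | -3.1% | -4.7% |

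- **Other statistics, n = 4.** The geometric mean, which SAP 3.1 allows for PK variables, shifts by 2^(1/4) - 1 = +18.9% (day 14) or 0.25^(1/4) - 1 = -29.3% (day 56). The median of (1, 1, 1, 2) or (1, 1, 1, 0.25) stays at 1.
- **Half-life.** With an assumed 7 days, the ratios are 2^(14/7) = 4.0 at day 14 and 2^(-28/7) = 0.06 at day 56. In a cell of 4 the mean then shifts by (4 - 1)/4 = +75% or (0.06 - 1)/4, about -23%.
- **Antibody comparison.** Suppose true exposure is identical and antibody-negative samples are all troughs. If 2 of 4 antibody-positive values are ET samples, the positive/negative ratio of means is (2 + 2 x 2.0)/4 = 1.50 at day 14, or (2 + 2 x 0.25)/4 = 0.63 at day 56. If ET samples have the same share and timing in both groups, the ratio is 1.

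**The case against.** The strongest reply is that this is an open detail rather than a chosen faulty analysis. Protocol 13 leaves detail to the SAP, the SAP does not carry the mapping forward, and the meaning of the next nominal visit is not settled. This stands in part: pooling with troughs is conditional. But Protocol 13.2 is the only rule stated, it has no PK exception, and silence in the SAP does not withdraw it.

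It can also be said that the consequence is limited. The summaries are descriptive, all data are listed, draw times are recorded, and the median resists a single outlying value. This stands and sets the severity.

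A reader might infer more than the documents support:

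- **That Completion samples are pooled too, so that all 16 subjects contribute one.** The rule names withdrawal visits. Treatment also ends by design, at age 18 or on US pediatric approval, and nothing maps those visits. The number of early withdrawals is not given.
- **That the antibody comparison is biased, in a known direction.** Nothing shows that ET samples differ in share or timing by antibody status, and the shift can go either way.
- **That the Week 0 value is a mid-interval sample because "First study drug administration occurs 2 weeks later (Week 2".** This depends on the C87035 dosing schedule, which the documents do not give, and PK sampling in this study starts at Week 14.
- **That a low value after a missed dose is the same artefact.** It reflects genuinely lower exposure.
- **That only samples at 28 +/-7 days should be kept.** With windows of +/-7 days relative to entry, consecutive visits can be 14 to 42 days apart and still comply. Such a filter would discard compliant samples.

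**Conclusion.** The concern holds in limited form. Followed as written, Protocol 13.2 can place an untimed ET concentration among predose troughs, and no PK text prevents it. Under the 14-day half-life model, one such sample in a cell of 4 moves the arithmetic mean by +25% (day 14) to -19% (day 56); in a cell of 16 the shift is about +6% to -5%. These figures rest on a healthy-volunteer half-life, no absorption phase, equal true exposure and assumed ET days. They illustrate sensitivity and do not predict the result. Distortion of the antibody-status comparison is possible but not shown. The point is minor: it affects the reading of a descriptive secondary objective and leaves the safety objective untouched.

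**What to change.** Add to SAP 10.1:

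1. CZP concentrations are exempt from the withdrawal-visit mapping in Protocol 13.2.
2. By-visit concentration summaries include only scheduled predose samples.
3. ET and Completion concentrations are presented in a separate summary or listing, with days since last dose.

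Days since last dose is the draw date minus the last dose date. Protocol 11 records the date and time of each draw, Protocol 7.2 asks for the date and time of home doses, and SAP 7 already uses the last dose date. No new data are needed. The cost is a short text change, one derived variable and slightly fewer values in some visit cells.
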